4 STUDY POPULATION

4.1 Disease definition

[....]

Included in the study may be cases of bulbar-onset and spinal-onset ALS. Cases with only bulbar signs or symptoms for the first three months from onset, with spinal symptoms or signs occurring later, are considered bulbar onset ALS. Cases in which any spinal symptoms or signs appeared in the first three months are considered spinal onset ALS. Bulbar onset and spinal onset ALS will be considered separately at the analysis stage.

Patients not fulfilling the diagnostic criteria as indicated in the protocol cannot be enrolled.

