11.2 Statistical Analysis Plan

The study will use a modified intent to treat approach with all patients included who took at least one dose of the study medication or placebo. The primary analysis, described below, is valid as long as the probability of non-observation of a data point is independent of the value that would have been observed conditional on the previous observed data. In the case of ALSFRS this method has been shown to be robust (Ref <http://www.ncbi.nlm.nih.gov/pubmed/22987690>). Separate analyses will be performed in: 1. All randomized subjects receiving at least one dose of study medication (Intention-to-treat population); 2. Study completers: subjects completing the 12-month follow-up; 3. Study completers and compliers: subjects completing the 12-month follow-up and taking at least 75% of assigned dose. 4. All randomized subjects excluding protocol deviations (Per protocol, PP population). Descriptive statistics will be performed comparing the two treatment groups and safety of RNS60 and placebo. Continuous variables will be described using mean and standard deviation or median and interquartile range; categorical variables will be described as counts and percentages.

Biomarkers analysis:

The primary analysis will be a repeated measures analysis of variance (ANOVA) with a treatment variable that is the same for all treatments at baseline and then differs at later observation times. We will use an unstructured variance covariance matrix. The contrast of interest will depend on the outcome. Note that this is more general than a random effects model in situations where the observation times are fixed. For biomarkers that progress over time such as Cyp-A, the primary analysis will compare the rate of change in the biomarker over time in the placebo and active treatment groups. In biomarkers that do not progress but rather are elevated in patients, the primary analysis will be a comparison in the treatment effect. Both of these analyses are contrasts in a repeated measures ANOVA, the former by treatment \times time, and the latter being treatment \times (time>0). Each biomarker will be analyzed separately.

Efficacy analysis:

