The numerical change of FVC, ALSFRS-R and ALSAQ-40 during the treatment and follow-up period will be assessed using repeated measures ANOVA, with an unspecified variance covariance matrix. The hypothesis will be tested using the time*treatment interaction which measures differences in the slope of the ALSFRS-R. Survival (time to death or tracheostomy) and time to functional disability (i.e., to reach a non self-supporting status or death or tracheostomy) will be assessed using actuarial methods with death and non-self supporting status as end-points. Survival will be described with the Kaplan-Meier method. Differences between the two treatment groups will be compared using the log-rank test. The statistical significance will be set at the 0.05 level for a two-tailed test.

The repeated measures ANOVA will use all available data, using Maximum Likelihood methods as suggested by (<http://www.nap.edu/read/12955/chapter/1>).

Safety analysis will be performed in all subjects receiving at least one dose of the experimental drug. All AEs, SAEs and AEs leading to treatment discontinuation will be recorded, listed and compared in the two treatment arms at any follow-up visit and at the end of the study. The number of patients reporting at least one AE or SAE will be compared between the treatment arms using the fisher exact test. The total number of AE and SAE will be compared between the treatment arms using a poisson model. MedDRA code system will be used for all recorded AE/SAE.

Given the exploratory value of this study, multiple comparison adjustments for Type I errors will not be considered as a more conservative significance level would lead to miss any potential treatment effect. Furthermore, if there is a suggestive benefit ($p<0.1$) in the clinical measures and several of the biomarkers, this will be considered sufficient evidence for further study.

If at the end of the patient enrolment period less than 50% of patients are enrolled, an interim-analysis will be performed to decide whether or not to continue the trial.

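### Section 11.2 fits its repeated-measures models by maximum likelihood with no small-sample correction: standard errors are slightly too small at 142 patients, and clearly so only if the model is used in about 70 patients or fewer

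*Combined protocol and SAP*

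**What the plan says.** Section 11.2 analyses the biomarkers, FVC, ALSFRS-R and ALSAQ-40 by repeated measures ANOVA. The biomarker model has "a treatment variable that is the same for all treatments at baseline and then differs at later observation times", so the arms share a baseline mean. For its covariance the plan says "We will use an unstructured variance covariance matrix"; the clinical scales are analysed "with an unspecified variance covariance matrix", which I read as the same thing. Biomarkers are tested either as treatment by time or as treatment by (time>0), and "Both of these analyses are contrasts in a repeated measures ANOVA".

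The estimator is named once, under the efficacy analysis: "The repeated measures ANOVA will use all available data, using Maximum Likelihood methods". The biomarker paragraph uses the same name for its analysis, so I take the sentence to cover both. The level is set as follows: "The statistical significance will be set at the 0.05 level for a two-tailed test". REML, Kenward-Roger, Satterthwaite and degrees of freedom are not mentioned, and neither is the type of test (Wald or likelihood ratio).

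Smaller sets also appear. Section 11.2 lists completers, completers who took at least 75% of dose, and a per-protocol set. Section 4.1 adds: "Bulbar onset and spinal onset ALS will be considered separately at the analysis stage". Section 11.2 ends with a conditional look: "If at the end of the patient enrolment period less than 50% of patients are enrolled, an interim-analysis will be performed". No size is given for the completer, complier, per-protocol or onset sets. The interim is bounded by its trigger, at under 50% of 142, that is under 71 patients.

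**The concern.** Maximum likelihood divides by the number of patients without allowing for the estimated means, so its covariance estimate is biased low. The usual Wald standard error also treats that estimate as known. Both errors grow as the covariance gains parameters relative to patients. An unstructured matrix for v visits has v(v+1)/2 parameters: 10 for the four biomarker visits to week 24, 15 for all five, 21 for the six ALSFRS-R and FVC visits (screening set aside), and 6 for the three ALSAQ-40 visits.

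The result is standard errors that are too small and p-values that are too low against the two-sided 0.05 level. Section 11.2 also treats p<0.1 in the clinical measures and several biomarkers as enough to go on to further study, so calibration matters at that threshold too. Declining a multiplicity adjustment is a stated choice in this exploratory trial; a miscalibrated single test is not.

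**Working it through.** **Inputs.** From section 11.1: 142 patients; drop-out 1.75% per month; ALSFRS-R random-effect variances 31.8 (intercept) and 0.6687 (slope), covariance 0.8527, error variance 2.7. From section 6.7: 1:1 allocation. From section 11.2: the mean model, covariance and level above. Assumed: normal data; ALSFRS-R variances used for every setting, because no biomarker covariance is given; 40 patients as an illustrative onset subgroup.

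**The plan's own figures.** No stated figure is in dispute. As a check, T-reg with difference 0.25 and SD 0.5 needs 2 × (1.96 + 0.8416)² × 0.5² / 0.25² = 62.8, so 63 per arm and 126 in total by the normal formula. The two-sample t calculation gives 128, as stated. It also reproduces the stated MCP-1, Actin-NT, 3-NT and Cyp-A totals. The sample sizes thus already allow for estimating the variance.

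**Size of the completer set.** 142 × (1 − 0.0175)^12 = 142 × 0.809 = 115.

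**Null simulation.** 3,000 runs per setting. The 142-patient setting has drop-out at 1.75% per month; the others are complete. Each cell gives: ML standard error divided by Kenward-Roger standard error; type I error (%) of ML with a Wald z test; type I error (%) of REML with Kenward-Roger standard error and Satterthwaite degrees of freedom. Monte Carlo error is √(0.05 × 0.95/3000) = 0.4 points near 5%.

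| Model and contrast | n=142 | n=114 | n=70 | n=40 |
|---|---|---|---|---|
| 6 visits, one linear treatment × time term | 0.956; 6.8; 5.6 | 0.950; 6.6; 5.0 | 0.920; 8.8; 5.8 | 0.867; 10.4; 5.4 |
| 6 visits, slope contrast of visit-specific effects | 0.984; 5.6; 5.0 | 0.982; 5.6; 5.1 | 0.971; 7.0; 5.8 | 0.950; 6.8; 4.6 |
| 4 visits, linear | 0.970; 6.3; 5.2 | 0.966; 6.6; 5.6 | 0.945; 7.4; 5.8 | 0.906; 8.1; 5.1 |
| 4 visits, treatment × (time>0) | 0.972; 6.0; 5.0 | 0.966; 7.0; 5.6 | 0.945; 6.4; 4.9 | 0.906; 8.9; 5.6 |
| 5 visits, linear | 0.963; 5.8; 5.0 | 0.958; 7.1; 5.8 | 0.932; 7.0; 4.9 | 0.886; 10.7; 6.3 |

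The ML standard error is therefore too small by 1.6-4.4% at 142, 1.8-5.0% at 114, 2.9-8.0% at 70 and 5.0-13.3% at 40. At the p<0.1 threshold, ML with Wald z rejects in 11.0-12.6% of null runs at 142 and 12.3-16.8% at 40.

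**Closed-form check (complete data, two arms).** Let k be the number of visits minus the number of free treatment effects. Then

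expected ML variance / true variance = [(n−2−k)/n] × [(n−3−k)/(n−3)].

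- 6 visits, one linear term (k=5), n=142: (135/142)(134/139) = 0.9165, square root 0.957.
- Same, n=70: (63/70)(62/67) = 0.8328, square root 0.913.
- Same, n=40: (33/40)(32/37) = 0.7135, square root 0.845.
- 6 visits, visit-specific effects (k=1), n=142: (139/142)(138/139) = 0.9718, square root 0.986; n=40: 0.900, square root 0.949.

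The type I error of the Wald z test is the chance that |t| on n−2−k degrees of freedom exceeds 1.96 × √[(n−2−k)/n] / √(1+Q), averaged over Q = [k/(n−1−k)] × F(k, n−1−k). For k from 1 to 5 this gives 5.5-6.3% at 142, 5.7-6.6% at 115, 6.1-7.9% at 70 and 7.1-10.7% at 40, in line with the simulation. No variance term enters, so with complete data the result depends neither on the missing biomarker covariances nor on the time unit of the slope variance, which the plan does not state.

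**Which part of the fix does the work.** At 142, REML alone raises the standard error by about 0.7% (√(142/140) = 1.007) and leaves type I error at 5.4-6.7%. Adding Kenward-Roger brings it to 5.0-5.6%.

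**The case against.** The strongest reply is that the plan does not name a Wald z test. The Maximum Likelihood sentence concerns using all available data and cites a missing-data source, so it may be a family term that does not exclude REML. A separate check on complete data (3,000 runs; correlation 0.5 assumed for the level contrast) shows that the test matters:

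| Test with ML | n=142 | n=114 | n=70 | n=40 |
|---|---|---|---|---|
| Wald z | 5.8-6.4% | 5.7-6.4% | 6.5-6.9% | 8.8-9.6% |
| t on n−2 df | 5.7-6.2% | 5.5-6.1% | 6.0-6.6% | 7.7-8.8% |
| Likelihood ratio | 5.4-6.1% | 5.1-6.0% | 5.4-5.8% | 6.7-7.4% |

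This stands: a literal reading of the plan can be close to nominal at 70. It does not close the point, because the test is left open, and reading the phrase as REML would not by itself restore the level.

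A reader might infer that standard errors are clearly too small in all the smaller sets. The documents do not support that. Completers are the only one of the listed analysis sets whose size follows from the plan's figures, and they are barely worse off than the full set. The complier and per-protocol sizes are unknown.

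A reader might also infer a badly inflated bulbar-onset result or interim decision. Section 4.1 gives no model, test or size for the onset groups. The interim is conditional and has no stated endpoint or test. With an assumed 28 patients (20% of 142), a six-visit slope under ML with Wald z reached 16.4%, but the plan describes no such analysis.

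Nor does the further-study rule rest on one subgroup p-value: it asks for signals in clinical measures and several biomarkers together.

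**Conclusion.** The point holds as a minor one. The plan names an estimator that, with Wald inference and an unstructured covariance, understates standard errors by about 2-4% at 142 patients and gives about 5.6-6.8% type I error at a nominal 5%. Completers (about 115) are much the same. The error is clear only if this model is carried into about 70 patients or fewer: roughly 6.4-8.8% at 70 and 7-11% at about 40.

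The size depends on the contrast: it is least for a slope built from visit-specific effects and greatest for one linear term over six visits. It rests on Wald z tests, normal data and, for the smallest sets, sizes and models that the documents do not give. It would not by itself overturn the full-set conclusions of an exploratory trial.

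**What to change.** In section 11.2, replace the phrase naming Maximum Likelihood with: using restricted maximum likelihood (REML) with Kenward-Roger standard errors and degrees of freedom. Say that this applies to every repeated-measures model and analysis set, including the onset groups and any interim if they use these models. Prespecify a simpler fallback covariance for small sets or non-convergence. It is needed because, with 28 patients and six visits, REML with Kenward-Roger still gave 7.7%.

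The cost is one or two sentences and a standard software option. No new data are needed, and validity under the plan's missing-data assumption is kept. In the full set, standard errors grow by 1.6% (1/0.984) to 4.6% (1/0.956), and the t multiplier on about 132 degrees of freedom adds just under 1%, so intervals are a few per cent wider.

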2.4 Secondary Endpoints

1. The mean change in the proportion of T-reg (measured via FOXP3 and CD25 mRNA); the mean change over time in the plasma concentrations of Cyp-A, 3-NT, Actin-NT, MCP-1, IL-17 during the follow up period (from 24 to 48 weeks);
2. The cumulative proportion of subjects becoming no longer self-sufficient at 4, 12, 24, 36 and 48 weeks in the two treatment arms (defined as those scoring 2 or lower on at least one of the ALSFRS-R items for swallowing, cutting food and handling utensils, or walking);
3. The mean change of ALSFRS-R total score in the two treatment arms during the treatment and follow up period;
4. The cumulative proportion of deaths or tracheostomies in the two treatment arms during the entire study including follow-up;
5. The mean change of FVC score in the two treatment arms during the treatment and follow up period;
6. The total number of subjects in the two treatment arms experiencing at least one AE leading to treatment discontinuation at 4, 12 and 24 weeks;
7. The mean number of AEs per treatment arm at 4, 12, 24 and 48 weeks;

8. The mean change of ALSAQ-40 score measuring quality of life at the completion of the treatment and follow up period.

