6.11 Premature Subject Withdrawal

The duration of the study includes 24 weeks of treatment plus 24 weeks of follow up. Subjects may voluntarily withdraw from the study or can be dropped at the discretion of the investigator at any time. Subjects must be withdrawn from the study if any of the following occurs:

- Unwillingness to comply with procedures as outlined in the study protocol;
- Withdrawal of consent;
- Loss to follow-up;
- Repeated non-compliance to dosing regimen or visit schedule (intake of 50% of recommended dose or less in three consecutive intervals between visits);
- Intolerable adverse events which may or may not be related to study medication and, if deemed drug-related, non remitting with down titration;
- Death/Tracheostomy;
- Requirement of medication doses greater than those allowable in the study;
- Abnormal laboratory value(s) deemed of medical concern;
- Administrative problems;
- Female becoming pregnant;
- Severe protocol deviations (at the Study Coordinator judgment).

If a subject withdraws or fails to return for visits, the investigator must determine the primary reason for the subject's premature withdrawal from the study, and record this information on the study-completion visit. Subjects must return all unused/remaining study drug to the investigative site. For subjects who are lost to follow up, the investigator should show "due diligence" by documenting in the source documents the steps taken to contact the subject, e.g., dates of telephone calls, registered letters, etc. Subjects who are prematurely withdrawn from the study will not be replaced.

Discontinued use of riluzole during the treatment period implies the discontinuation of the experimental drug. The subject will undergo a final safety evaluation and data collected up to the time of drug discontinuation will be used in the data analysis.

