9.2 Adverse Events

The Investigator is responsible for recording all AEs observed during the study.

For expected (listed) AEs of RNS60, see the current version of the IB.

All AEs will be collected starting from the signing of informed consent through the infusion visits and the follow up. During this period the investigator is responsible for reporting to the sponsor all non-serious AEs, SAEs occurring in subjects treated by the investigator in the clinical trial.

AEs (but not SAEs) occurring before starting study treatment but after signing the informed consent form are recorded on the Medical History/Current Medical Conditions Case Report Form.

[...]

Investigators must code the grade of all AEs occurring during the trial. For more detail about grade criteria, refer to “Common Terminology Criteria for Adverse Events (CTCAE)” Version 4.0 Published: May 28, 2009 (v4.03: June 14, 2010) from the U.S. DEPARTMENT OF HEALTH AND HUMAN SERVICES National Institutes of Health National Cancer Institute.

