9.3 AE Reporting

All AEs, regardless of severity and whether or not they occurred during the treatment or follow-up period, are to be recorded on the appropriate AE pages in the e-CRF. The investigator will include the date of onset and duration of the AE, as well as the severity and causality of each AE, and the actions taken. Each event should be recorded separately.

[...]

In case of patients needing a Non Invasive Ventilation (NIV), it is necessary to record the procedure into the AE form.

The investigator shall report all AEs and DAEs into the e-CRF, without reporting to “Mario Negri” IRCCS.

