9.4 Reporting of SAEs and SUSARs

[...]

The following serious events should not be recorded as SAE due to the usual progression of the disease and the investigator judgment:

- Death (only if caused by the disease progression);
- Tracheotomy;
- PEG/RIG placement.

If these events occur, the Investigator must record them into the AE form.

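### Minor: the Poisson comparison of total AEs and SAEs states no allowance for overdispersion or unequal observation time, so a default fit would give p-values that are too small if counts vary more than Poisson

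*Combined protocol and SAP*

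**What the plan says.** The safety paragraph of section 11.2 plans two comparisons. Patients with at least one AE or SAE are compared by Fisher exact test. For totals: "The total number of AE and SAE will be compared between the treatment arms using a poisson model". No offset, person-time, robust variance, quasi-Poisson or negative binomial method appears in the visible text. The safety set is everyone with at least one dose.

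The related provisions are:

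- **Endpoint.** Section 2.4, item 7: "The mean number of AEs per treatment arm at 4, 12, 24 and 48 weeks".
- **What is counted.** Section 9.3: "Each event should be recorded separately", and "In case of patients needing a Non Invasive Ventilation (NIV), it is necessary to record the procedure into the AE form". Section 9.4 lists progression death, tracheotomy and PEG/RIG placement under the rule "The following serious events should not be recorded as SAE due to the usual progression of the disease and the investigator judgment", then adds "If these events occur, the Investigator must record them into the AE form". These events therefore enter the AE count but not the SAE count.
- **How long patients are observed.** Follow-up lasts at most 48 weeks and stops at death or tracheotomy (section 3). Stopping study drug early counts as withdrawal from the study (6.10). Mandatory withdrawal reasons include "Intolerable adverse events which may or may not be related to study medication" (6.11).
- **When counting starts.** Section 9.2: "AEs (but not SAEs) occurring before starting study treatment but after signing the informed consent form are recorded on the Medical History/Current Medical Conditions" form. Section 11.2 gives no start date for the counts.

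**The concern.** A plain Poisson model takes the variance of each patient's count to equal its mean. Two features of this trial work against that.

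First, NIV, PEG/RIG placement and a terminal tracheotomy or death can all come from one patient's disease course, and each is a separate entry. Second, patients are observed for different lengths of time, which adds variance to the counts even if every patient has the same underlying rate. Either way the Poisson standard error is too small, and a chance imbalance in total AEs could be reported as a significant harm or benefit.

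A separate issue is bias. Without an offset, the ratio of counts departs from the ratio of rates if observation time, or its relation to AE risk, differs between arms.

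Safety and tolerability is a secondary objective, and the AE count is a named secondary endpoint at four time points.

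**Working it through.** The plan states no figure for this comparison, so there is nothing to reproduce. Every event rate and dispersion below is an assumption.

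**Inputs from the documents.** 71 patients per arm (sections 3, 6.7). Two-sided 0.05: section 11.2 gives this in its efficacy paragraphs, and I take it to apply here. Drop-out 1.75% per month (11.1): 1 − 0.9825^6 = 10.05%, matching the stated 10%. I extend that rate to 48 weeks (48 × 12/52 = 11.08 months), giving 17.8% loss.

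**Assumed.** 4 AEs per patient over 48 weeks at a constant rate, exponential drop-out, and a gamma frailty (a patient multiplier with mean 1 and variance k).

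**Step 1: size for a given variance/mean ratio φ.** Size = 2 × [1 − Φ(1.96/√φ)]. For φ = 1, 1.5, 2 and 3 this is 5.0%, 11.0%, 16.6% and 25.8%.

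**Step 2: φ at 48 weeks.** Let m1 and m2 be the mean and mean square of the observed fraction of 48 weeks. With L = −ln(0.9825) and T = 11.08 months:

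- m1 = (1 − e^(−LT))/(LT) = 0.908
- m2 = 2[1 − e^(−LT)(1 + LT)]/(LT)² = 0.879
- φ = 1 + 4 × [(1 + k) × m2 − m1²]/m1

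This gives φ = 1.24, 2.20 and 3.17 for k = 0, 0.25 and 0.5, hence sizes of 7.8%, 18.7% and 27.1%.

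**Step 3: simulation.** 20,000 trials, no true difference, equal drop-out.

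| AEs, k = 0 / 0.25 / 0.5 | 24 weeks | 48 weeks |
|---|---|---|
| Plain Poisson | 5.4% / 11.4% / 16.9% | 8.0% / 18.4% / 27.0% |
| Offset only | 4.6% / 10.9% / 16.6% | 5.2% / 15.9% / 25.5% |
| Offset + sandwich errors | about 5% to 6% | about 5% to 6% |

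At k = 0 the 8% comes from unequal follow-up alone, and the offset removes it. The offset does not cure overdispersion; the robust variance does. At k = 1 the corrected test still runs at about 6%.

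**Step 4: SAEs at 48 weeks, plain Poisson.**

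| SAEs per patient | Size |
|---|---|
| 0.1 | 3.0% to 3.5% (k = 0 to 1) |
| 0.3 | 4.9%, 5.9%, 6.2%, 8.2% (k = 0, 0.25, 0.5, 1); 11.5% (k = 2) |
| 0.5 | 10.4% (k = 1), 16.1% (k = 2) |

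**Step 5: bias in the count ratio.** True rate ratio 1.00.

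- Drop-out 1% vs 2.5% per month, unrelated to AE risk: mean observed time at 48 weeks is 10.48 vs 9.66 months, so the ratio without an offset is 9.66/10.48 = 0.92. At 4, 12 and 24 weeks it is 0.99, 0.98 and 0.96.
- Drop-out 1.75% in both arms but AE-related in one only (k = 0.5): 0.96 at 48 weeks, with or without the offset.

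**Step 6: can an SAE rate ratio be estimated early?** At 0.1 SAEs per patient over 48 weeks, at least one arm has no SAE in about 80% of trials at 4 weeks and about a third at 12 weeks. At 0.3 per patient it is 32% and 1%.

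**The case against.** The best reply is that this is silence, not error. A Poisson model can carry an offset and robust errors, and section 11.2 excludes neither. That stands: a reader might infer that the plan commits to an unadjusted fit, and the text does not say so. The sizes above apply only if the default is run.

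Nor do the documents show that AE counts are overdispersed. Entry criteria narrow the population (self-sufficient, FVC at least 80% of predicted, 6 to 24 months from onset). Tracheotomy and death end follow-up, so the linked progression entries are few: NIV, PEG/RIG and one terminal event. This limits the clustering argument but leaves the unequal-follow-up part untouched.

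Other tempting readings also fail:

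- **That SAEs are little affected, or affected as much as AEs.** No SAE rate is given. Excluding progression events from SAEs lowers the count but does not fix its level, and the result runs from no inflation to 16% over the range examined.
- **That the count ratio is biased only if drop-out rates differ by arm.** Step 5 gives 0.96 with equal rates.
- **That the missing start date is a serious gap.** Pre-dose AEs already go to medical history. Randomization and first dose share Day 1, so nearly all pre-dose SAEs precede randomization and cannot differ systematically by arm.

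The Fisher test is immune to repeat events, which softens the consequence. It still depends on observation time: with 1% vs 2.5% drop-out, 4 AEs per patient and k = 0.5, the expected proportions with at least one AE at 48 weeks are 86.5% and 83.0%.

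**Conclusion.** The point holds as a minor, inexpensive improvement. The model is underspecified, and its default form would be too liberal for total AEs whenever per-patient counts vary more than Poisson. The figures of about 8%, 18% and 27% at 48 weeks rest on an assumed 4 AEs per patient, gamma frailty and equal exponential drop-out; the closed form and the simulation agree. For SAEs the effect can be stated only conditionally on their rate.

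A reader might infer that this undermines the trial's conclusions. It does not. The study is exploratory, AEs are also listed and compared by patient, and the stated criterion for further study uses clinical measures and biomarkers, not AE counts.

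**What to change.** In section 11.2, replace the sentence on totals with:

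> The number of AEs and, separately, of SAEs per patient with onset from first dose will be compared between arms by Poisson regression with robust (sandwich) standard errors and the log of each patient's observation time as offset. The rate ratio and 95% CI will be reported for AEs at 4, 12, 24 and 48 weeks and for SAEs at 48 weeks. SAEs at earlier time points will be given as counts only, and if an arm has no events the comparison will rest on the Fisher exact test.

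Keep the mean number of AEs per arm (2.4, item 7) as a descriptive summary.

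**Cost.** A few sentences, settled before unblinding. No new data: AE assessment is scheduled at every visit from baseline on, including the drop-out visit (Table 2), and onset dates are recorded (9.3).

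**Downsides.**

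- Log-scale intervals widen when counts are overdispersed: for k = 0.25 and 0.5, by a factor of 1.21 and 1.39 at 24 weeks and 1.38 and 1.68 at 48 weeks.
- Size stays slightly above 5% with strong clustering (about 6% at k = 1).
- The offset does not remove bias when drop-out is related to AE risk. With 1% vs 2.5% drop-out proportional to frailty (k = 0.5), the 48-week ratio moves only from 0.89 to 0.96.
- The offset also assumes a roughly constant AE rate. If the rate on treatment is twice that in follow-up, with 1% vs 2.5% drop-out unrelated to AE risk, the ratio is 0.93 without it and 1.01 with it.
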